11. MEASUREMENT OF EFFECT

11.1 Antitumor Effect – Solid Tumors

For the purposes of this study, patients should be re-evaluated for response every eight weeks. In addition to a baseline scan, confirmatory scans should also be obtained not less than 4 weeks following initial documentation of objective response.

Response and progression will be evaluated in this study using the new international criteria proposed by the revised Response Evaluation Criteria in Solid Tumors (RECIST) guideline (version 1.1) [*Eur J Ca* 45:228-247, 2009].

Changes in the largest diameter (unidimensional measurement) of the tumor lesions and the shortest diameter in the case of malignant lymph nodes are used in the RECIST criteria.

11.1.1 Definitions

Evaluable for toxicity: All patients will be evaluable for toxicity from the time of their first treatment with MK-2206.

Evaluable for objective response: Only those patients who have measurable disease present at baseline, have received at least one cycle of therapy, and have had their disease re-evaluated will be considered evaluable for response. These patients will have their response classified according to the definitions stated below. (Note: Patients who exhibit objective disease progression prior to the end of cycle 1 will also be considered evaluable.)

Evaluable Non-Target Disease Response: Patients who have lesions present at baseline that are evaluable but do not meet the definitions of measurable disease, have received at least one cycle of therapy, and have had their disease re-evaluated will be considered evaluable for non-target disease. The response assessment is based on the presence, absence, or unequivocal progression of the lesions.

11.1.2 Disease Parameters

Measurable disease: Measurable lesions are defined as those that can be accurately measured in at least one dimension (longest diameter for non-nodal lesions and short axis for nodal lesions to be recorded) as ≥ 20 mm by chest x-ray, as ≥ 10 mm with CT scan, or ≥ 10 mm with calipers by clinical exam. All tumor measurements must be recorded in millimeters (or decimal fractions of centimeters).

Note: Tumor lesions that are situated in a previously irradiated area might or might not be considered measurable.

Malignant lymph nodes: To be considered pathologically enlarged and measurable, a lymph node must be ≥ 15 mm in short axis when assessed by CT scan (CT scan slice thickness recommended to be no greater than 5 mm). At baseline and in follow-up, only the short axis will be measured and followed.

Non-measurable disease: All other lesions (or sites of disease), including small lesions (longest diameter < 10 mm or pathological lymph nodes with ≥ 10 to < 15 mm short axis), are considered non-measurable disease. Bone lesions, leptomeningeal disease, ascites, pleural/pericardial effusions, lymphangitis cutis/pulmonitis, inflammatory breast disease, and abdominal masses (not followed by CT or MRI), are considered as non-measurable.

Note: Cystic lesions that meet the criteria for radiographically defined simple cysts should not be considered as malignant lesions (neither measurable nor non-measurable) since they are, by definition, simple cysts.

‘Cystic lesions’ thought to represent cystic metastases can be considered as measurable lesions, if they meet the definition of measurability described above. However, if non-cystic lesions are present in the same patient, these are preferred for selection as target lesions.

Target lesions: All measurable lesions up to a maximum of 2 lesions per organ and 5 lesions in total, representative of all involved organs, should be identified as **target lesions** and recorded and measured at baseline. Target lesions should be selected on the basis of their size (lesions with the longest diameter), be representative of all involved organs, but in addition should be those that lend themselves to reproducible repeated measurements. It may be the case that, on occasion, the largest lesion does not lend itself to reproducible measurement in which circumstance the next largest lesion which can be measured reproducibly should be selected. A sum of the diameters (longest for non-nodal lesions, short axis for nodal lesions) for all target lesions will be calculated and reported as the baseline sum diameters. If lymph nodes are to be included in the sum, then only the short axis is added into the sum. The baseline sum diameters will be used as reference to further characterize any objective tumor regression in the measurable dimension of the disease.

Non-target lesions: All other lesions (or sites of disease) including any measurable lesions over and above the 5 target lesions should be identified as **non-target lesions** and should also be recorded at baseline. Measurements of these lesions are not required, but the presence, absence, or in rare cases unequivocal progression of each should be noted throughout follow-up.

Measurable disease. Measurable lesions are defined as those that can be accurately measured in at least one dimension (longest diameter to be recorded) as ≥ 20 mm by chest x-ray or as ≥ 10 mm with CT scan, MRI, or calipers by clinical exam. All tumor measurements must be recorded in millimeters (or decimal fractions of centimeters).

Note: Tumor lesions that are situated in a previously irradiated area might or might not be considered measurable. *If the investigator thinks it appropriate to include them, the conditions under which such lesions should be considered must be defined in the protocol.*

Malignant lymph nodes. To be considered pathologically enlarged and measurable, a lymph node must be ≥ 15 mm in short axis when assessed by CT scan (CT scan slice thickness recommended to be no greater than 5 mm). At baseline and in follow-up, only the short axis will be measured and followed.

Non-measurable disease. All other lesions (or sites of disease), including small lesions

(longest diameter <10 mm or pathological lymph nodes with ≥ 10 to <15 mm short axis), are considered non-measurable disease. Bone lesions, leptomeningeal disease, ascites, pleural/pericardial effusions, lymphangitis cutis/pulmonitis, inflammatory breast disease, and abdominal masses (not followed by CT or MRI), are considered as non-measurable.

Note: Cystic lesions that meet the criteria for radiographically defined simple cysts should not be considered as malignant lesions (neither measurable nor non-measurable) since they are, by definition, simple cysts.

‘Cystic lesions’ thought to represent cystic metastases can be considered as measurable lesions, if they meet the definition of measurability described above. However, if non-cystic lesions are present in the same patient, these are preferred for selection as target lesions.

Target lesions. All measurable lesions up to a maximum of 2 lesions per organ and 5 lesions in total, representative of all involved organs, should be identified as **target lesions** and recorded and measured at baseline. Target lesions should be selected on the basis of their size (lesions with the longest diameter), be representative of all involved organs, but in addition should be those that lend themselves to reproducible repeated measurements. It may be the case that, on occasion, the largest lesion does not lend itself to reproducible measurement in which circumstance the next largest lesion which can be measured reproducibly should be selected. A sum of the diameters (longest for non-nodal lesions, short axis for nodal lesions) for all target lesions will be calculated and reported as the baseline sum diameters. If lymph nodes are to be included in the sum, then only the short axis is added into the sum. The baseline sum diameters will be used as reference to further characterize any objective tumor regression in the measurable dimension of the disease.

Non-target lesions. All other lesions (or sites of disease) including any measurable lesions over and above the 5 target lesions should be identified as **non-target lesions** and should also be recorded at baseline. Measurements of these lesions are not required, but the presence, absence, or in rare cases unequivocal progression of each should be noted throughout follow-up.

11.1.3 Methods for Evaluation of Measurable Disease

All measurements should be taken and recorded in metric notation using a ruler or calipers. All baseline evaluations should be performed as closely as possible to the beginning of treatment and never more than 4 weeks before the beginning of the treatment.

The same method of assessment and the same technique should be used to characterize each identified and reported lesion at baseline and during follow-up. Imaging-based evaluation is preferred to evaluation by clinical examination unless the lesion(s) being followed cannot be imaged but are assessable by clinical exam.

Clinical lesions: Clinical lesions will only be considered measurable when they are superficial (e.g., skin nodules and palpable lymph nodes) and ≥ 10 mm diameter as assessed using calipers (e.g., skin nodules). In the case of skin lesions, documentation by color photography, including a ruler to estimate the size of the lesion, is recommended.

Chest x-ray: Lesions on chest x-ray are acceptable as measurable lesions when they are clearly defined and surrounded by aerated lung. However, CT is preferable.

Conventional CT and MRI: This guideline has defined measurability of lesions on CT scan based on the assumption that CT slice thickness is 5 mm or less. If CT scans have slice thickness greater than 5 mm, the minimum size for a measurable lesion should be twice the slice thickness. MRI is also acceptable in certain situations (e.g. for body scans).

Use of MRI remains a complex issue. MRI has excellent contrast, spatial, and temporal resolution; however, there are many image acquisition variables involved in MRI, which greatly impact image quality, lesion conspicuity, and measurement. Furthermore, the availability of MRI is variable globally. As with CT, if an MRI is performed, the technical specifications of the scanning sequences used should be optimized for the evaluation of the type and site of disease. Furthermore, as with CT, the modality used at follow-up should be the same as was used at baseline and the lesions should be measured/assessed on the same pulse sequence. It is beyond the scope of the RECIST guidelines to prescribe specific MRI pulse sequence parameters for all scanners, body parts, and diseases. Ideally, the same type of scanner should be used and the image acquisition protocol should be followed as closely as possible to prior scans. Body scans should be performed with breath-hold scanning techniques, if possible.

PET-CT: At present, the low dose or attenuation correction CT portion of a combined PET-CT is not always of optimal diagnostic CT quality for use with RECIST measurements. However, if the site can document that the CT performed as part of a PET-CT is of identical diagnostic quality to a diagnostic CT (with IV and oral contrast), then the CT portion of the PET-CT can be used for RECIST measurements and can be used interchangeably with conventional CT in accurately measuring cancer lesions over time. Note, however, that the PET portion of the CT introduces additional data which may bias an investigator if it is not routinely or serially performed.

Ultrasound: Ultrasound is not useful in assessment of lesion size and should not be used as a method of measurement. Ultrasound examinations cannot be reproduced in their entirety for independent review at a later date and, because they are operator dependent, it cannot be guaranteed that the same technique and measurements will be taken from one assessment to the next. If new lesions are identified by ultrasound in the course of the study, confirmation by CT or MRI is advised. If there is concern about radiation exposure at CT, MRI may be used instead of CT in selected instances.

Endoscopy, Laparoscopy: The utilization of these techniques for objective tumor

evaluation is not advised. However, such techniques may be useful to confirm complete pathological response when biopsies are obtained or to determine relapse in trials where recurrence following complete response (CR) or surgical resection is an endpoint.

Tumor markers: Tumor markers alone cannot be used to assess response. If markers are initially above the upper normal limit, they must normalize for a patient to be considered in complete clinical response. Specific guidelines for both CA-125 response (in recurrent ovarian cancer) and PSA response (in recurrent prostate cancer) have been published [*JNCI* 96:487-488, 2004; *J Clin Oncol* 17, 3461-3467, 1999; *J Clin Oncol* 26:1148-1159, 2008]. In addition, the Gynecologic Cancer Intergroup has developed CA-125 progression criteria which are to be integrated with objective tumor assessment for use in first-line trials in ovarian cancer [*JNCI* 92:1534-1535, 2000].

Cytology, Histology: These techniques can be used to differentiate between partial responses (PR) and complete responses (CR) in rare cases (e.g., residual lesions in tumor types, such as germ cell tumors, where known residual benign tumors can remain).

The cytological confirmation of the neoplastic origin of any effusion that appears or worsens during treatment when the measurable tumor has met criteria for response or stable disease is mandatory to differentiate between response or stable disease (an effusion may be a side effect of the treatment) and progressive disease.

FDG-PET: While FDG-PET response assessments need additional study, it is sometimes reasonable to incorporate the use of FDG-PET scanning to complement CT scanning in assessment of progression (particularly possible 'new' disease). New lesions on the basis of FDG-PET imaging can be identified according to the following algorithm:

- a. Negative FDG-PET at baseline, with a positive FDG-PET at follow-up is a sign of PD based on a new lesion.
- b. No FDG-PET at baseline and a positive FDG-PET at follow-up: If the positive FDG-PET at follow-up corresponds to a new site of disease confirmed by CT, this is PD. If the positive FDG-PET at follow-up is not confirmed as a new site of disease on CT, additional follow-up CT scans are needed to determine if there is truly progression occurring at that site (if so, the date of PD will be the date of the initial abnormal FDG-PET scan). If the positive FDG-PET at follow-up corresponds to a pre-existing site of disease on CT that is not progressing on the basis of the anatomic images, this is not PD.
- c. FDG-PET may be used to upgrade a response to a CR in a manner similar to a biopsy in cases where a residual radiographic abnormality is thought to represent fibrosis or scarring. The use of FDG-PET in this circumstance should be prospectively described in the protocol and supported by disease-specific medical literature for the indication. However, it must be acknowledged that both approaches may lead to false positive CR due to limitations of FDG-PET and biopsy resolution/sensitivity.

- d. AKT inhibition inhibits cellular membrane glucose transporters, so that alterations in FDG uptake may demonstrate a pharmacodynamic activity of MK-2206, but may not correlate with antitumor activity.

Note: A 'positive' FDG-PET scan lesion means one which is FDG avid with an uptake greater than twice that of the surrounding tissue on the attenuation corrected image.

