13. STATISTICAL CONSIDERATIONS

13.1 Study Design/Endpoints

This is an open-label, multi-center, randomized phase II study. Patients will be randomized using 2:1 ratio to receive either MK2206 or everolimus. The primary endpoint of the study is progression-free survival (PFS), where an event is defined as either disease progression or death. The anticipated median PFS is 4.9 months and 8.2 months for the everolimus and MK2206 arms, respectively. The secondary endpoints include safety, overall survival (OS), overall response rate (ORR) and time to failure (TTF). For the primary endpoint, one interim futility analysis will be performed when a total of 38 events have occurred. The O'Brien-Fleming stopping boundaries using Lan-DeMets spending function will be used for early rejection of H1 (futility boundaries). At the interim look, if the nominal critical point (Z-scale) is less than 0.051, we will terminate trial, reject H1, and conclude that MK2206 has no significant effect on improving PFS. Assuming that the alternative hypothesis holds and trial is continued to completion without interim analysis, 105 patients with 75 events provide 81% power to reject null hypothesis. Since this trial has one interim analysis, 105 patients with 75 events provide 80% power to reject null hypothesis. Please see the detail information for power calculation in [section 13.2](#) sample size / power calculation.

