13.2 Sample Size/ Power Calculation

Assuming that the median progression-free survival (PFS) is 4.9 months and 8.2 months for the everolimus and MK2206 arm, respectively and patients will be randomized with 2:1 ratio into the MK2206 arm and the everolimus arm, then with a total of 75 events (i.e., disease progression or death), we will have an 80% power to detect such a 67% increase in median PFS using one-sided log-rank test and at a 0.10 significance level. The total number of patients to be enrolled will be 105, with 35 on the everolimus arm and 70 on the MK2206 arm. The above calculation also assumes an accrual rate of 4 patients per month, thus it will take 26.3 months to accrue all 105 patients. The maximum study duration will be around 29 months, which include patients' accrual period and a follow-up period. East5 software was used for the sample size/power calculation.

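### Section 11.1.3 lets unscheduled FDG-PET establish and date progression while warning that MK-2206 alters FDG uptake, so PFS ascertainment could differ between arms by an unknown amount

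*Combined protocol and SAP*

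**What the plan says.** The FDG-PET part of section 11.1.3 allows PET to complement CT in assessing progression, and lists four items.

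- Item a: "Negative FDG-PET at baseline, with a positive FDG-PET at follow-up is a sign of PD based on a new lesion". No CT confirmation is stated.
- Item b covers patients with no baseline PET. A new PET-positive site needs CT confirmation. If CT does not confirm it at once, follow-up CT decides, and a progression found that way takes the date of the first abnormal PET. Uptake at a known site that is anatomically stable is not PD.
- Item c: "FDG-PET may be used to upgrade a response to a CR in a manner similar to a biopsy", for a residual abnormality thought to be fibrosis or scarring. The item adds that such use should be set out in advance in the protocol with disease-specific literature behind it, and it warns of false-positive CR.
- Item d: because AKT inhibition acts on glucose transporters, "alterations in FDG uptake may demonstrate a pharmacodynamic activity of MK-2206, but may not correlate with antitumor activity".

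A closing note defines a positive lesion as one with more than twice the uptake of surrounding tissue.

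Sections 11.1.4.1 and 11.1.4.2 count any new lesion as PD, and section 13.1 makes PFS the primary endpoint of an open-label trial. FDG-PET is not named among the baseline or on-study assessments in section 5.2, nor in the study calendar (section 10).

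**The concern.** Items a to c read as general response-criteria rules. Item d is specific to this trial and states a reason not to rely on those rules here, but nothing follows from it. An investigator cannot tell whether a PET finding counts toward the endpoints.

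The route into the primary endpoint is direct. A PET-positive new lesion can be PD under item a, and PET can move the PD date earlier under item b. If treatment lowers uptake in one arm more than in the other, the same lesion may be called or dated differently by arm with no difference in tumor growth. PET is ordered at the discretion of investigators who know the assignment. The PET-CT paragraph of the same section itself warns that PET information not obtained routinely or serially may bias the reader. No blinded central review of progression is described; section 11.1.4.2 mentions only a review panel or the Principal Investigator, for progression in non-target lesions.

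**Working it through.** **1. The plan's own design figure.** Inputs from sections 13.1 and 13.2: "The anticipated median PFS is 4.9 months and 8.2 months for the everolimus and MK2206 arms, respectively"; "Patients will be randomized using 2:1 ratio to receive either MK2206 or everolimus"; the test is made "using one-sided log-rank test and at a 0.10 significance level"; and, without the interim look, "105 patients with 75 events provide 81% power to reject null hypothesis".

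- Hazard ratio = 4.9/8.2 = 0.598; |ln HR| = 0.515.
- Schoenfeld power = Φ(√(75 × 2/3 × 1/3) × 0.515 − 1.282) = Φ(2.102 − 1.282) = Φ(0.820) = 79.4%, against 81% stated.
- Events for 80% power = (1.282 + 0.842)² / (2/9 × 0.515²) = 76.5, so 77, against 75 stated.
- Observed hazard ratio needed for significance at 75 events = exp(−1.282/4.082) = 0.73.

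The design reproduces to within rounding and method. No figure in the plan is in dispute here.

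**2. Which PET rules can act on PFS.**

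- Item a can act without CT, but only where a baseline PET was done. None is scheduled, so this needs an ad hoc scan.
- Item b needs CT to establish PD, but PET can set the date. It needs no baseline PET.
- Item c concerns CR and does not bear on PFS.
- Item d limits none of them.

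**3. Simple size calculation (assumption: the PET-led fraction f is not in the documents).** Suppose a fraction f of everolimus progressions is called by PET one 8-week visit earlier than CT would call it, that this never happens on MK-2206, and that the arms do not truly differ.

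- One visit = 56/30.44 = 1.84 months.
- Mean control PFS, exponential = 4.9/ln 2 = 7.07 months.
- f = 0.10: loss 0.184 months; apparent control hazard × 7.07/(7.07 − 0.184) = 1.027.
- f = 0.20: loss 0.368 months; 7.07/(7.07 − 0.368) = 1.055.
- f = 0: no change.

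**4. Simulation of the test (same kind of assumption, expressed as a delay on MK-2206).** Both medians are 4.9 months, with 70 and 35 patients, "an accrual rate of 4 patients per month", scans every 8 weeks, analysis at the 75th event, no interim look, an unstratified log-rank test and 4,000 runs per row. A fraction f of MK-2206 progressions is recorded one scan late.

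| f | Rejection rate at nominal one-sided 0.10 | Apparent hazard ratio (no true effect) |
|---|---|---|
| 0 | 0.106 | 1.00 |
| 5% | 0.119 | 0.98 |
| 10% | 0.132 | 0.97 |
| 20% | 0.166 | 0.94 |
| 30% | 0.204 | 0.91 |

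The simulation error is about √(0.10 × 0.90/4,000) = 0.005, so the first row is consistent with 0.10. With the planned medians and f = 0, the same program gives 80.8% power, which agrees with the plan.

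Steps 3 and 4 show what a one-sided shift would do. They are not evidence that it occurs.

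**The case against.** The strongest reply is that PET has little room to act. It is not scheduled, so item a will rarely apply. Without a baseline PET, item b requires CT confirmation. A lesion that PET misses can still be found on the scheduled CT in either arm, so a negative PET does not suppress a CT-based progression. Items c and d and the PET-CT paragraph already carry cautions. All of this stands. It limits the likely size, but it does not tell an investigator what to do with a PET that has been obtained, and the back-dating in item b needs no baseline scan.

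A reader might infer that the distortion is confined to the MK-2206 arm and must favor it. The documents do not support that. Section 6.1, on hyperglycemia, attributes inhibition of glucose transport to AKT/mTOR inhibitors together, which covers everolimus. Positivity is also a ratio to surrounding tissue, and the documents do not say how uptake in tumor changes relative to background. Equally, nothing shows that the two arms are affected alike.

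A reader might also infer from item c that false CRs would inflate the response rate, at 1/70 = 1.4 points per MK-2206 patient. This does not follow. The item's own condition is unmet, because the protocol neither describes this use for the trial nor gives renal-cancer support for it. The item speaks of upgrading a response, most naturally PR to CR, and section 13.4 defines overall response as CR+PR, so such a change leaves ORR as it was. Only an SD-to-CR upgrade would move it, and item c does not describe one.

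**Conclusion.** The point holds as a gap in how the primary endpoint is ascertained, not as a numerical error or a demonstrated bias. Items a and b let PET establish or date progression; item d says why PET is unreliable under MK-2206, and constrains neither.

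The direction plausibly favors MK-2206, because suppressed uptake would mean fewer or later PET-led calls, but it is not established. The size is unknown. Under the assumption of PET-led calls on everolimus only, at 10% to 20% of its progressions and a full visit early, the apparent control hazard rises by about 2.7% to 5.5%. In the matching simulation the nominal 0.10 error becomes 0.13 to 0.17. These shifts are small beside the hazard ratio of 0.73 needed for significance, and they shrink to nothing as PET use falls. It would be wrong to read the simulated error rates as the trial's actual type I error.

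The case for acting rests on the low cost and on protecting the primary endpoint. It does not depend on the direction or on a proven effect.

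**What to change.** In section 11.1.3, state that:

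- FDG-PET alone may not establish PD or CR in either arm;
- a PET finding triggers CT/MRI;
- PD raised by a PET finding is assigned, and dated, only on the CT/MRI assessment.

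Remove item a as a stand-alone PD rule, the back-dating clause in item b, and item c, whose condition is not met. Keep item d as the stated reason. The existing provisions for the other scheduled imaging need not change, and the diagnostic-quality CT part of a PET-CT can still serve as CT under the section's present terms.

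If PET has already informed any PD call, add a sensitivity analysis of PFS using CT/MRI-based calls and dates only, and report by arm how many calls changed.

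The cost is about one paragraph of protocol text, plus that analysis if it is needed. CT/MRI restaging is already planned every 8 weeks (12 weeks is permitted for patients progression-free after one year). The downside is that progressions first seen on PET will be dated somewhat later, and not necessarily in equal numbers in the two arms.
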